10.2 Secondary & Exploratory Efficacy Analysis

Secondary efficacy analyses will be based on the ITT population only. Continuous endpoints will be analyzed using the MMRM analysis. The mean changes from baseline will be analyzed using a restricted maximum likelihood (REML) based repeated measures approach. Analyses will include the fixed, categorical effects of population source, center and study week as well as the fixed covariates of baseline score and baseline score-by-study week interaction. An unstructured covariance structure will be used to model the within-patient errors. If this analysis fails to converge, the following structures will be tested: first order ante dependence, heterogeneous first order autoregressive, heterogeneous compound symmetry and compound symmetry. The covariance structure converging to the best fit, as determined by Akaike's information criterion, will be used in the analysis (Mallinckrodt et al, 2008). The Kenward-Roger approximation will be used to estimate the denominator degrees of freedom. Significance test will be based on least-squares means using a two-sided $\alpha=0.05$ test and two-sided 95% confidence intervals will be presented. The comparison of interest is the contrast between the weeks of challenges and baseline.

[figure not shown]
MMRM analysis will be implemented with a modified baseline observation carried forward (BOCF)/last observation carried forward (LOCF) algorithm. Where the study medication was discontinued due to lack of efficacy or to an AE or the cause is unknown, the baseline value is used for all values after the last date that study medication was taken (as shown in the Daily Diary). If the study medication was discontinued for any other reason, then the last observation will be carried forward. This is an MNAR analysis that investigates changes in endpoints using logical assumptions. Assessment values collected after treatment discontinuation, and true missing values (after withdrawal from the study) will be imputed in this manner.

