### **2.2.2 Secondary Endpoints**

Secondary efficacy endpoints include:

- Comparative estimates of changes in immune parameters over time among subjects who were induced with clinical desensitization versus those who failed. Changes coinciding with the loss of desensitization would also be studied.
- Incidence of all adverse events and serious adverse events during the study.
- Incidence of all gastrointestinal and possible gastrointestinal eosinophilic adverse events.

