## **7. MECHANISTIC ASSAYS**

Complementary studies will be performed to measure cellular and humoral immune responses at baseline and longitudinally. These assays have been selected based on hypothesized mechanisms of clinical desensitization induction.

Early data demonstrates that desensitization with peanut SLIT alters both humoral and cellular parameters [23]. We anticipate that peanut SLIT will induce clinical tolerance and SU by either (1) a conversion from a Th2 to Th1 immune response or (2) the induction of TRegs or (3) a combination of both. Subjects will be followed for changes in immunologic parameters at baseline and then yearly with additional studies at the 48 month desensitization DBPCFC and post-avoidance SU DBPCFC. Immunologic assays will focus on peanut specific parameters including: 1) basophil activation and skin prick testing; 2) humoral studies - specific IgE, IgG, IgG4, and IgA; and 3) cellular studies – Treg activation and T cell-stimulated cytokine production.

Briefly, PBMC's will be isolated from blood drawn at yearly time points and cultured with crude peanut extract (CPE)[31], tetanus toxin, and Con A to assess cellular proliferation responses. A control proliferation assay using nonstimulated cells will also be performed. In addition, cultures will be set up to assess cytokine production by PBMC's after stimulation with CPE, tetanus toxin, ConA and control. Culture supernatants will be analyzed yearly for the levels of the following cytokines: IFN- $\gamma$ , IL-4, IL-5, IL-10, IL-13, TGF- $\beta$  and TNF- $\alpha$ . Using flow cytometry, we will determine the presence of TRegs in the blood sample each year. Basophil studies will be performed annually to examine activation markers. Salivary and serum peanut specific antibody levels, including IgE, IgG, IgG4, and IgA will be assessed annually.

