3.2.3 Endpoint Definitions

- The loss of desensitization is defined as the decline in sensitivity threshold at the final DBPCFC from the 48th month DBPCFC.
- NOAEL is the highest dose observed not to produce any adverse effect and LOAEL is the lowest dose that is observed to produce an adverse effect. Experimentally determined individual's true sensitivity threshold lie between NOAEL and LOAEL. The establishment of individual NOAELs and LOAELs is dependent upon the selection of and spacing between doses selected in the clinical challenge trial design.

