4.3 Method of Week Assignment for the Final Challenge and Randomization

The following criteria must be satisfied in order for the patient to continue to the SU phase of the study and be randomized:

1. The patient achieves MCRT at the 48th month DBPCFC to continue to the SU phase. This requires patient to be asymptomatic upon administration of 300 mg dose as assessed by Food Challenge Symptom Score sheet.
2. If subjects are found symptomatic and AEs that occur are considered to be intolerable at or below the MCRT, subjects will be refrained from taking the final challenge and will be considered to have lost their desensitization at week 0.
3. No subject will be administered a final challenge dose higher than the NOAEL attained at the 48th month DBPCFC.

Before the start of the SU phase of the study, a computer-generated block randomization schedule is prepared such that each subject has an equal probability of being randomized to one of the weekly challenges held in initial 6 weeks, between 7-12 weeks and between 13-17 weeks. Based on the randomization schedule, three qualified subjects are randomly assigned to one of the final DBPCFC administered each week during the study's 17-week SU phase.

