8. GENERAL ISSUES FOR STATISTICAL ANALYSIS

8.1 General Statistical Methodology

Descriptive summaries will be provided where appropriate for each of the primary and secondary variables.

Baseline characteristic and safety tables will be completed for the Safety Population unless otherwise specified. Baseline values are defined as the last non-missing measurement prior to the first dose of study drug. Change from baseline will be defined as the post-baseline visit value minus the baseline value.

Continuous, quantitative, variable summaries will include the number of patients (N) with non-missing values, mean and standard deviation, median, minimum, and maximum. Categorical, qualitative, variable summaries will include the frequency and percentage of patients who are in the particular category. In general the denominator for the percentage calculation will be based upon the total number of patients in the study population unless otherwise specified.

Efficacy tables will be presented for the ITT Population for each of the primary objectives. First, the number and proportion of subjects for each interval of NOAEL and LOAEL observed at the 48th month DBPCFC will be reported. This will be broken by baseline and other clinical characteristics. Non-parametric Kaplan-Meier estimates of NOAEL distribution with interval censoring will be used to report expected proportion of subjects within each interval of NOAEL and LOAEL, overall and by patient groups. Second, for each interval of NOAEL and LOAEL observed at the 48th month DBPCFC, Kaplan-Meier product limit estimates of the probabilities of loss of tolerance (as defined by the latter three efficacy outcomes in section 3.2.1 bullet 2) using interval censoring, will be plotted against time (17 weeks), overall and for various patient groups. The “expected” number of patients with loss of tolerance and the “P values” derived

from univariate log rank tests for interval censored data will be reported for each 48th month DBPCFC NOAEL.

Unless otherwise indicated, all statistical tests will be 2 sided and tested at a significance level of 0.05. Corresponding 95% confidence intervals will be presented for statistical tests.

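### The immune-parameter MMRM contrasts challenge weeks with pre-SLIT baseline and has no term for loss of desensitization, so it does not estimate the protocol's endpoint on immune changes accompanying that loss

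*SAP*

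**What the plan says.** - **Endpoint.** Protocol 2.2.2 adds to the immune-parameter endpoint: "Changes coinciding with the loss of desensitization would also be studied". The synopsis and Objective #3 repeat it. SAP 3.2.1 leaves it out, and no other SAP section analyses it.
- **Loss.** SAP 3.2.3: "The loss of desensitization is defined as the decline in sensitivity threshold at the final DBPCFC from the 48th month DBPCFC".
- **Sampling.** Protocol section 7 has immune samples taken "at baseline and then yearly with additional studies at the 48 month desensitization DBPCFC and post-avoidance SU DBPCFC". Appendix 1 has a single post-avoidance column, at a randomly selected week from 1 to 17. SAP 4.3 spreads the children thinly: "three qualified subjects are randomly assigned to one of the final DBPCFC administered each week". SAP 4.2 could be read as weekly challenges, but SAP 4.3 and Appendix 1 give each child one.
- **Model.** SAP 10.2: "Analyses will include the fixed, categorical effects of population source, center and study week as well as the fixed covariates of baseline score", together with a baseline-by-week interaction and an unstructured covariance. Four simpler structures are listed in case of non-convergence. The target is "The comparison of interest is the contrast between the weeks of challenges and baseline".
- **Reference.** SAP 8.1: "Baseline values are defined as the last non-missing measurement prior to the first dose of study drug".
- **Carry-forward.** The last paragraph of SAP 10.2 replaces values recorded after treatment stops with the baseline or last value. It does not say whether the scheduled stop of SLIT counts.

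**The concern.** Loss is defined between the 48th month and final challenges, so the immune change that goes with it runs between the same two visits. The planned contrast starts at least 48 months earlier, before any SLIT. It adds the whole on-treatment effect, and four or more years of growing up, to a short off-drug change. Nothing in the model separates children who lost desensitization from those who kept it. A marker that falls once SLIT stops could still be reported as raised, and the trial would have no pre-specified answer to which markers move with loss, which is part of Objective #3. A second question is whether a categorical week effect suits a design in which no child is sampled at two avoidance weeks.

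**Working it through.** Neither document gives a sample size, SD or effect size for this analysis, so there is no plan figure to reproduce. The 50 subjects in Protocol 8.1.1 belong to the superseded two-arm comparison.

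**Inputs.** On-treatment visits: 12, 24, 36 and 48+ months (Appendix 1). Avoidance weeks: 1 to 17. Children: 17 × 3 = 51 (SAP 4.3), or about 45 (Protocol 5.2). Assumed: 35 as a low case; 30-70% losing desensitization; results in SD units.

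**1. What the contrast contains.** Let b, m and p be a child's values before SLIT, at 48+ months and after avoidance. The planned contrast averages p − b = (m − b) + (p − m). The endpoint needs p − m, split by loss status. Hypothetical case: a marker rises 10-fold on SLIT and falls 20% off it. Then p/b = 10 × 0.8 = 8, so it is reported as 8-fold up although it fell.

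**2. Why the missing loss term matters.** Suppose SLIT shifts a marker by −1 and loss adds D. Averaged over weeks, the planned contrast is −1 + D × q, where q is the mean of 1 − (1 − s)^(t/9) over t = 1 to 17 and s is the share lost by week 9.
- D = 1.0, s = 0.50: q = 0.464, contrast = −1 + 0.464 = −0.54.
- D = 0.613, s = 0.865: q = 0.769, contrast = −1 + 0.613 × 0.769 = −0.53.

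Two clearly different loss effects give almost the same planned contrast. A simulation with three children per week (between-child SD 0.7, error SD 0.5) gave −0.54 and −0.53. The change from 48+ months, split by loss status, recovered 1.00 and 0.61.

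**3. Levels of study week.** The SAP does not list them.
- *17 separate weeks.* Levels: 4 + 17 = 21. Covariance parameters: 21 × 22/2 = 231 (21 variances, 210 covariances). Pairs of avoidance weeks: 17 × 16/2 = 136, and no child contributes to any of them. Children per week: 51/17 = 3, 45/17 = 2.65, 35/17 = 2.06. A mean and a baseline slope for each week make 34 parameters for 45 to 51 post-avoidance samples; a week with two children is fitted exactly. With three children and a known SD, a weekly mean has a 95% half-width of 1.96/√3 = 1.13 SD.
- *One pooled post-avoidance visit.* Levels: 5. Covariance parameters: 5 × 6/2 = 15, with every pair observed within children. The model can be fitted, but time off drug disappears and the reference is still b.

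**4. Carry-forward.** If planned withdrawal counts as stopping for another reason, p is replaced by the last on-drug value m, and p − m = 0 for every child whatever the truth.

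**5. Precision of a direct comparison.** The detectable difference in p − m at 80% power, two-sided 0.05, is (1.960 + 0.842) × √(1/n₁ + 1/n₂), with n₁ children losing and n₂ keeping desensitization.

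| Children | Lost / kept | Detectable difference (SD of change) | 95% half-width |
|---|---|---|---|
| 45 | 22 / 23 | 0.84 | 0.58 |
| 45 | 14 / 31 or 31 / 14 | 0.90 | 0.63 |
| 35 | 18 / 17 | 0.95 | 0.66 |
| 35 | 10 / 25 | 1.05 | 0.73 |

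These are unadjusted. Loss depends on weeks off drug, so adjusting for weeks costs some precision; adjusting for m may regain some.

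**The case against.** The best defence is that this is an omission and not a barrier. Each randomized child has both samples and a known loss status. The average off-drug change could be formed by subtracting two fitted means, since both are changes from the same baseline. SAP 8.2.2 speaks of annual samples plus the final challenge, and Appendix 1 has one post-avoidance column, so study week may well mean a nominal visit. Fallback covariance structures are listed. The endpoint is secondary, the protocol words it loosely, and the SAP permits labelled post-hoc analyses.

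Much of this stands, and it rules out three stronger readings that a reader might infer.
- That the change accompanying loss cannot be derived: it can, from scheduled data. One post-avoidance sample per child only prevents timing the immune change to the moment of loss.
- That the model cannot be fitted: this applies only to the unstructured matrix under the 17-week reading.
- That a trend in weeks is 2 to 4 times more precise than weekly means. With 45 children, the standard errors are 0.61 SD for a weekly mean and 0.15 to 0.29 SD for a straight line. But that line has no loss term, so the ratio does not carry over to the comparison needed here.

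What the defence does not answer is that the subtraction is unplanned and would still pool children who lost and kept desensitization. A post-hoc analysis is also weaker evidence than one named in advance.

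**Conclusion.** The point holds as a gap between endpoint and analysis. SAP 10.2 targets change from pre-SLIT baseline, with no 48+ month reference and no loss-status term, so no planned analysis estimates the immune changes that accompany loss of desensitization. This does not depend on how study week is read. The covariance count (136 of 231 parameters not estimable) does: it requires 17 separate week levels. The carry-forward problem likewise depends on treating planned withdrawal as discontinuation, which the SAP leaves open. No primary estimate is affected; the matter is worth correcting because the endpoint is stated and the samples are already scheduled. The precision figures assume 35 to 45 randomized children and 30-70% losing desensitization. A comparison by loss status is an association, since loss is not randomized.

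**What to change.** In SAP 10.2:
- Keep the MMRM for the on-treatment visits (12, 24, 36 and 48+ months) and list these as its time levels.
- For the avoidance phase, pre-specify the within-child change from the 48+ month sample to the post-avoidance sample, compared between children who lost and who kept desensitization as SAP 3.2.3 defines loss. Adjust for the 48+ month value and actual weeks off SLIT, either continuous or in the SAP 4.3 groups of weeks 1-6, 7-12 and 13-17. Name this as the analysis of the protocol endpoint, and restore that endpoint in SAP 3.2.1.
- State that planned SLIT withdrawal is not treatment discontinuation for the BOCF/LOCF rule, so that observed post-avoidance values are used.

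The cost is SAP wording only, with no new visits or samples. The downsides are an assumed trend or grouping in weeks (a quadratic term can check the trend) and modest precision: about 0.84-0.90 SD of the change is detectable with 45 children.

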7. ANALYSIS POPULATIONS

The following analysis populations are planned for this study:

- **Safety Population (SAFETY):** all patients who receive at least 1 dose of investigational product. All safety analyses and demographic/baseline characterization will be performed using this population, analyzed as treated.
- **Intention-To-Treat Population (ITT):** all patients who are randomized for assessment of clinical desensitization and SU. This population is primary for efficacy and all efficacy analyses will be performed using this population.

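### SAP 10.2 overwrites the off-drug immune values and has no term or population for the desensitized-versus-failed comparison

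*SAP*

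**What the plan says.** The endpoint has two parts. SAP 3.2.1 and Protocol 2.2.2 list a comparison of immune-parameter change over time between children who were desensitized and children who failed. Protocol 2.2.2 adds that immune changes accompanying loss of desensitization will be studied. Protocol 7, Appendix 1 and SAP 8.2.2 provide for sampling at the post-avoidance challenge as well as yearly.

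SAP 10.2 then sets out the analysis:

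- **Imputation.** "MMRM analysis will be implemented with a modified baseline observation carried forward (BOCF)/last observation carried forward (LOCF) algorithm". Baseline is carried forward after a stop for lack of efficacy, an adverse event or an unknown cause. For everything else: "If the study medication was discontinued for any other reason, then the last observation will be carried forward". Its reach is wide: "Assessment values collected after treatment discontinuation, and true missing values (after withdrawal from the study) will be imputed in this manner".
- **Population.** "Secondary efficacy analyses will be based on the ITT population only". SAP 7 defines ITT as "all patients who are randomized for assessment of clinical desensitization and SU".
- **Model.** "Analyses will include the fixed, categorical effects of population source, center and study week", together with baseline score and its interaction with study week.
- **Contrast.** "The comparison of interest is the contrast between the weeks of challenges and baseline".

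SAP 4.3 makes reaching the MCRT at month 48 a condition of randomisation ("The following criteria must be satisfied in order for the patient to continue to the SU phase of the study and be randomized"), and Protocol 5.5 likewise randomises the desensitized children. Protocol 8.1.2 gives the same MMRM with no carry-forward.

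**The concern.** There are two separate defects.

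(a) **Carry-forward.** Every randomised child stops SLIT for 1 to 17 weeks by design, and SAP 1 itself describes this as discontinuing SLIT. A planned stop is not lack of efficacy, an adverse event or an unknown cause, so the literal text sends it to LOCF. The value measured off drug is then discarded in favour of the last one measured on drug. The sample drawn to show what happens as protection wanes cannot contribute.

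(b) **Group comparison.** The only stated contrast is within-child over time, and no model term separates desensitized from failed children. If ITT follows SAP 4.3, there are also no failed children in the data set, so adding a status term alone would not help.

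At stake is a result reported as no immune change off drug that the imputation itself created, and a listed secondary endpoint for which the pre-specified model yields no estimate. Later analyses are allowed but must be labelled post hoc (SAP 2 and 5.2), which does not replace a pre-specified estimate.

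**Working it through.** **The plan's own figure.** Neither document gives a sample size or detectable effect for this endpoint. The only computed size, 50, belongs to the superseded two-arm design (Protocol 8.1.1). It reproduces with 90% versus 50%, two placebo per SLIT, two-sided 0.05 and 80% power. The pooled proportion is (0.9 + 2 × 0.5)/3 = 0.633. SLIT n = [1.96√(0.633 × 0.367 × 1.5) + 0.842√(0.09 + 0.25/2)]² / 0.4² = 14.96, taken as 15. Then 15 + 30 = 45, and 45/0.9 = 50. It does not bear on the point here.

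**Inputs.** 51 enrolled (SAP 1 and 6); 10% drop-out (Protocol 5.2 and 8.1.1); two-sided 0.05 (Protocol 8). The documents give no month-48 failure rate, so 10% to 40% is assumed. 51 × 0.9 = 45.9, taken as 46 month-48 challenges.

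**(a) Effect of the rule.** Let Y0, Y48 and YF be the baseline, month-48 and post-avoidance values. LOCF sets YF = Y48 (month 48 is ordinarily the last on-drug value).

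- Change since SLIT stopped: Y48 − Y48 = 0 for each child. Any difference between children who lost desensitization and those who kept it is 0 with zero variance.
- Modelled final change from baseline: Y48 − Y0, the month-48 result repeated. If a fraction r of the month-48 change reverses off drug, the true final change is (1 − r) of it, and the reported one is 1/(1 − r) times too large. For assumed r = 0.25, 0.50 and 0.75 that is 1.33, 2 and 4.
- The month-48 and final changes are identical, so their correlation is 1 and the planned unstructured covariance is singular for that pair.

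**(b) What the group comparison could deliver.** For n_f failed and n_d desensitized children, SE = √(1/n_f + 1/n_d), in units of the SD of change from baseline. With n_f + n_d − 2 = 44 degrees of freedom, 80% power on a two-sample t test needs a noncentrality of 2.865, so the detectable difference is 2.865 × SE.

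| Assumed failure | Failed | Desensitized | SE (SD) | Detectable (SD) | Failed in ITT under SAP 4.3 |
|---|---|---|---|---|---|
| 10% | 5 | 41 | 0.474 | 1.36 | 0 |
| 20% | 9 | 37 | 0.372 | 1.06 | 0 |
| 30% | 14 | 32 | 0.320 | 0.92 | 0 |
| 40% | 18 | 28 | 0.302 | 0.87 | 0 |

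The desensitized column is also the number of final values per parameter overwritten under (a): 28 to 41. The detectable differences apply only if failed children are analysed and a status contrast exists. As written, no contrast exists whichever children are in ITT.

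**The case against.** It can be argued that the carry-forward paragraph was meant for premature stops. Its list of reasons suits them. Protocol 3.3.1 lets children who stop early stay in follow-up, which gives an ordinary meaning to values collected after discontinuation. The same section names challenge weeks against baseline as its contrast, and overwriting the final challenge would empty half of that. The preceding paragraph specifies an MMRM without imputation, and the carry-forward paragraph calls itself an MNAR analysis, so it may have been intended as a robustness check. This is a plausible reading of intent. But the text does not limit the rule, does not label it a sensitivity analysis, and says that the MMRM will be implemented with it. The defect stands as the literal reading, and Protocol 8.1.2 and SAP 10.2 still differ.

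On ITT, SAP 4 can be read as randomising everyone at the month-48 visit, and SAP 8.1.2 and 10.1 keep failed children in the time-to-loss analysis at time zero. Whether ITT contains failed children is therefore unsettled. Even if it does, the model has no between-group term.

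Some limits are fair. Values taken on drug, including month 48, are untouched by (a). The off-drug element is in the protocol's endpoint list but not the SAP's. The failure and reversal rates are assumptions. Protocol 5.2 expects about 45 children eligible for randomisation, but that allows only for drop-out, not for failing the challenge. It also excludes one exception participant from analysis, which would move 46 to 50 × 0.9 = 45. Baseline adjustment would reduce the residual SD and so the detectable difference.

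**Conclusion.** Both defects hold as the SAP is written. (a) On the literal rule, every randomised child's post-avoidance immune value is replaced: 28 to 41 per parameter if 10% to 40% of about 46 children fail at month 48. The change since stopping is 0 by construction, and the final change from baseline is overstated 1.33 to 4 times if 25% to 75% of the month-48 change reverses. (b) The model cannot produce the desensitized-versus-failed estimate under any reading of who is randomised, and under SAP 4.3 none of the 5 to 18 failed children is in the analysis set. Once corrected, the comparison would detect only large differences, about 0.87 to 1.36 SD, so it is an estimation exercise. These are secondary endpoints; the primary and safety analyses are unaffected. The point should be fixed before analysis.

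**What to change.** Amend SAP 10.2 as follows, and bring Protocol 8.1.2 into line.

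1. State that the planned SLIT stop is not a discontinuation for imputation purposes, and use all observed values, including those at the post-avoidance challenge. Limit BOCF/LOCF to premature discontinuation, as a sensitivity analysis.
2. For desensitized versus failed, analyse all children with a month-48 challenge instead of ITT. Add month-48 status and status-by-visit, with visits through month 48 only, because failed children have no final visit. Name the month-48 status contrast in change from baseline as the endpoint estimate, with its 95% confidence interval.
3. For loss of desensitization, take the children who had the final challenge and regress their observed month-48-to-final change on loss status and weeks off SLIT. Name the loss event. A fall of one or more LOAEL levels can be read directly from the two challenges. Other models would serve; what matters is that one is pre-specified on observed data.

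The cost is SAP wording, a separate analysis set for this endpoint and a few degrees of freedom. No new samples or visits are needed. The failed group may be small, so the result should be reported as an estimate with its interval.
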